7.8 Integrated Summaries

For the final analysis (i.e., when the last subject in Stage 2 completed the Week 96 visit), a number of integrated summaries will be provided. These outputs will include 4 columns: one for each of the treatment arms 1, 3 and 4 and one for the TDF containing arms (arms 2 and 5) combined.

The following information will be summarized:

- Week 96 subject status (see [Section 7.3.1](#))
- Demography and baseline disease characteristics (see [Section 7.3.2.1](#))
- Baseline resistance (see [Section 7.3.2.4](#)):
 - The number of treated subjects with phenotypic resistance using the earlier mentioned mutually exclusive categories, and by class and drug name.
 - The genotypic resistance profile for all treated subjects.
 - The baseline gag polymorphisms at selected positions.
- Time on study therapy (see [Section 7.4.1](#))
- Newly emergent resistance for treated subjects with on-treatment resistance testing done (see [Section 7.5.2.5](#)):
 - Newly emergent phenotypic resistance profile
 - Newly emergent phenotypic resistance to BMS-955176
 - Newly emergent genotypic substitutions
 - Newly emergent Gag polymorphisms at the selected positions
 - Any newly emergent deviation from the wild type virus in Gag sequencing
- Safety (see [Section 7.6](#)):
 - Overall AE summary
 - SAEs

- AEs leading to discontinuation
- Grade 2-4 related AEs
- Grade 3-4 AEs
- CDC Class C events
- Gastrointestinal events
- Grade 3-4 laboratory toxicities

7.9 Outcomes Research

7.9.1 EQ-5D-3L

As described in the SAP for BMS study CN162-007, the EuroQol (EQ-5D-3L) provides a simple but effective standardized measure of a subject's quality of life and health state classification². It is intended to provide both a compact descriptive profile and a single index value that will be used in the clinical and economic evaluation of health care. The questionnaire consists of 2 parts, which together are used to build a composite picture of the respondent's health status.

In the first part, the "health state classification", the respondent is asked to indicate his/her current health state, by ticking the most appropriate of three statements about each of the 5 quality of life dimensions: mobility, self-care, usual activity, pain/discomfort, and anxiety/depression. Each of the 3 statements represents an increasing level of severity (1 = no problem, 2 = some or moderate problems, 3 = unable, or extreme problems). The string of five numbers, one for each dimension, indicates the aggregate health state. For example: "11111" indicates perfect health and "33333" indicates the worst health state.

The second part, "Visual Analogue Scale Thermometer", evaluates the respondent's current health-related quality of life by means of a 20cm visual analogue scale (VAS) with endpoints at 100 (best imaginable health state) and 0 (worst imaginable health state).

The scores obtained from the 5 health state dimensions (first part of the questionnaire) will be converted to a US centric utility score based on the algorithm described by Shaw et al³. This utility score has range score from -0.019 (worse health state) to a maximum of 1.000 (best health state). [APPENDIX 4](#) contains SAS code for calculating the US centric EQ-5D-3L utility score.

The scores obtained from the 5 health state dimensions will also be converted to a UK centric utility score based on the algorithm described by Dolan⁴. [APPENDIX 5](#) contains SAS code for calculating the UK utility scores.

For both the US centric and UK centric utility scores, values and changes from baseline are summarized as continuous parameters at baseline and all applicable, on-treatment analysis visits. Subjects must have paired measurements at baseline and the analysis visit to be evaluable.

7.9.2 FAHI

The FAHI consists of 5 subscales: Physical Well-Being, Emotional Well-Being, Function and Global Well-Being, Social Well-Being, and Cognitive functioning. Each scale consists of a number of questions, each of which has 5 possible responses: 0, 1, 2, 3 and 4.

A detailed description of the FAHI structure and scoring algorithm is contained in internal BMS document, “FAHI Source Doc (16-DEC-2014).PDF”, which is available upon request. A summary of the scoring algorithm is provided below.

Negatively stated items are reversed by subtracting the response from 4. After reversing proper items, all subscale items are summed to a total which is the subscale score. Higher scores indicate better the quality of life. The score for each scale is the prorated sum of the items answered. Thus, if a scale has 10 items, and only 6 are answered, the results of the six questions answered are summed and multiplied by 10. The result is then divided by 6.

- The Physical Well-Being section of the questionnaire contains 13 questions, however only 10 of them are used in scoring the scale. These are questions GP1-GP7, BMT6, HI7 and HI12. Before computing the score for this scale, all of the responses are reversed by subtracting the response from 4.
- The Emotional Well-Being scale consists of 10 items. Before computing the score for this scale, all of the responses are reversed by subtracting the response from 4.
- The Function and Global Well-Being scale consists of 13 items. Only one item, GE3, is reversed before the scale is scored.
- The Social Well-Being scale consists of 8 items. None of these items are reversed before the scale is scored.
- The Cognitive Functioning scale consists of three items. Two of these items, HI8 and HI9, are reversed before the scale is scored.

The scoring of any of the FAHI sub-scales is only considered valid as long as more than 50% of the subscale questions have been answered.

The total score for the FAHI is the sum of prorated scores from each of the five subscales. The overall score for the FAHI is considered valid if all of the subscales are considered to be valid.

The analysis data set includes the overall score and each of the subscale scores by visit for each subject as well as indicator variables that show if the validity condition has been met for each of the subscales, as well as the FAHI overall. Calculations for the FAHI total score and subscale scores use only valid data.

FAHI total scores are summarized as continuous parameters at baseline and all applicable on-treatment analysis visits.

7.10 Pharmacokinetics

The following intensive PK parameters will be summarized (using mean, SD, median, minimum, maximum, geometric mean and %CV) for BMS-955176, DTG and ATV by treatment arm:

- C_{max} : maximum observed plasma concentration
- T_{max} : time of maximum observed plasma concentration
- C_{tau} : observed plasma concentration at the end of a dosing interval
- C_0 : observed pre-dose plasma concentration
- AUC(TAU) area under the concentration-time curve in one dosing interval

The Pharmacokinetic (PK) population will be used for all listings. Evaluable PK population will be used for summary statistics and statistical analyses.

Subject plasma concentration-time profiles will be listed and summarized by treatment arm and nominal collection time for each analyte. Plots of individual plasma concentration profiles over time will be provided. Overlay of individual plasma concentration profiles over time will be provided by treatment arm. Plots of mean (+SD) plasma concentration profiles versus time will be presented for each analyte, and all treatments will be superimposed on the same plot for the analyte.

All individual PK parameters will be listed for each analyte including any exclusions and reasons for exclusion from summaries. Summary statistics will be tabulated for each PK parameter by treatment arm. Geometric means and coefficients of variation will be presented for C_{max} , AUC(TAU), C_{tau} , and C_0 . Medians and ranges will be presented for T_{max} .

The effect of BMS-955176 on the exposure of DTG (in the presence of ATV/RTV 300/100mg) will be estimated by the geometric mean ratio, with 90% confidence interval, of the exposure data in Arm 1 over the reference ATV/r arm (Arm 2). These estimates will be generated using general linear models fitted to log-transformed data. The effect of BMS-955176 on the exposure of DTG (in the presence of ATV 400mg) will be estimated by the geometric mean ratio, with 90% confidence intervals, of the exposure data in Arm 3 and Arm 4, separately, over historical data. These estimates will be generated using general linear models fitted to log-transformed data.

The population PK, exposure-response and viral kinetic analyses will be described in a separate analysis plan. Intensive and sparse pharmacokinetic data will be used in population PK, PK/PD and PK/VK.

8 CONVENTIONS

8.1 Derivation of Baseline and On-Treatment Parameters Using Visit Windows

8.1.1 Baseline

Baseline parameters are derived from pre-treatment measurements. Pre-treatment measurements are included for subjects in the following ways:

- For treated subjects: measurements are included through the start of study therapy.
- For randomized subjects who never received study therapy: measurements are included through randomization.
- For enrolled subjects who were never randomized: all available measurements are included.

The following algorithm details the derivation of baseline parameters:

- CD4+ and CD8+ T-cells: the last value on or before the start of study therapy. If there are multiple measurements on the same day from central and local laboratories, then the value from the central laboratory is selected.
- Genotypic and phenotypic parameters: identified from the last typable resistance test on or before the start of study therapy. HIV subtype is identified from the first resistance test at which subtype was assessed. If there are multiple tests on the same day, the last test run is chosen.
- All other parameters: the last value measured on or before the start of study therapy is selected. If there are multiple measurements on the same day, the value with the latest entry date/time is chosen :
 - HIV-1 RNA: Values are assigned a value of 1 more (or 1 less) if an inequality “>” (“<”) is present. Values outside the upper (or lower) limit of quantification are assigned a value or 1 more (or 1 less) than the limit. Only values from the central laboratory will be used.

8.1.2 On-Treatment Parameters

Time is measured from the first dose of study therapy.

On-treatment parameters are derived from measurements after the start of study therapy through the last dose of study therapy plus 4 days for efficacy, biomarkers and outcomes research scales, plus 10 days for resistance parameters and plus 30 days for safety.

For the primary and secondary efficacy endpoints of proportion of subjects with plasma HIV-1 RNA < 40c/mL at Weeks 24, 48 and 96, the snapshot algorithm and related window definition will be applied. The snapshot windows shown in the [Table 8.1.2-1](#) below differ from those proposed by the FDA by 1 day. The FDA windowing appears to have the first study day as Day 0, while the table below has the first study day as Day 1.

The windows for other parameters are based on the midpoint between planned study visits. For analysis through Week 96, the visit windows are presented in the following table:

Table 8.1.2-1: Visit Windows

Visit	Target Day	HIV-1 RNA (Snapshot Algorithm)	Other Parameters
B/L	1		≤ 1
2	15		2 - 21
4	29		22 - 43
8	57		44 - 71
12	85		72 - 99
16	113		100 - 141
24	169	127 - 210 (18-30 wks)	142 - 197
32	225		198 - 253
40	281		254 - 309
48	337	295 - 378 (42-54 wks)	310 - 379
60	421		380 - 463
72	505		464 - 547
84	589		548 - 631
96	673	631-714 (90-102 wks)	632 - 715

Study days are calculated as:

- Measurement date - first date of study therapy + 1 day, if measurement date is on or after start date of study therapy.
- Measurement date - first date of study therapy, if measurement date is before start date of study therapy.

Weeks are study days divided by 7.

The following conventions are used to select the value to be used in the analysis:

- HIV-1 RNA: analysis of the proportion of subjects with plasma HIV-1 RNA < 40c/mL at Week 24, 48 and 96 use the last plasma HIV-1 RNA value in the pre-defined visit window following the snapshot algorithm. For all other analyses or summaries of HIV-1 RNA, the value in the visit window that is closest to the target day of the planned visit (as determined by the absolute differences in days between the planned visit and the assessment date) will be used. In case of ties between observations located on different sides of the target day, the earlier assessment will be used. In case of ties located on the same side of the target day

(i.e., more than one value for the same day but different time), the value with the earlier entry date/time will be used. Only values from the central laboratory will be used.

- Values are assigned a value of 1 more (or 1 less) if an inequality “>” (or “<”) is present. Values outside the upper (or lower) limit of quantification are assigned a value of 1 more (or 1 less) than the limit.
- For other laboratory and non-laboratory parameters: if a subject has more than one measurement included within a window, the assessment closest to the target day will be used. In case of ties between observations located on different sides of the target day, the earlier assessment will be used. In case of ties located on the same side of the target day (i.e., more than one value for the same day but different time), the value with the earlier entry date/time will be used.

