6 STUDY PERIODS, TREATMENT REGIMENS AND POPULATIONS FOR ANALYSES

6.1 Study Periods

This study consists of the following periods:

- Screening (or Pre-randomization) Period: begins on the day the subject signs the informed consent and continues through Day 1 prior to dosing. The screening period last about 42 days.
- Open-label Treatment Period (or On-treatment Period): begins on the first day of open-label therapy and ends after 96 weeks of dosing or early termination, whichever comes first.

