7.6 Safety

Safety endpoints include the frequency of adverse events (AEs), serious adverse events (SAEs), non-serious adverse events, CDC Class C AIDS events, adverse events leading to discontinuations, deaths and other significant adverse events as reported on case report forms. Other safety endpoints include laboratory abnormalities, changes in laboratory parameters, changes in vital signs and physical measurements, and ECGs. Safety endpoints will not be evaluated through a specific analysis week. All safety data available in the database at the time of the lock will be included.

Safety summaries are provided for treated subjects by as-treated treatment arm, unless otherwise specified.

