7.6.13.2 Laboratory Tests over Time

All summaries of laboratory data over time will use observed values. Visit windows are defined in [Section 8](#).

Observed values and changes from baseline in creatinine and creatinine clearance will be summarized at each scheduled visit by treatment arm.

Observed values, changes from baseline and percent changes from baseline will be summarized over time for the following laboratory tests:

- Fasting Total cholesterol,
- Fasting HDL-cholesterol
- Fasting LDL-cholesterol,
- Fasting Triglycerides.
- Total:HDL cholesterol ratio

Values obtained after the start of serum lipid-reducing agents will be excluded from these lipid summaries. Mean percent changes from baseline using observed values will be plotted at each scheduled visit with error bars representing 1 standard error of the reported statistic.

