3.18	Summary of Grade 3 to 4 Adverse Events Modified Treated Subjects	Table S.6.5.1D / rt-ae-grade3to4s1.lst / GS_AE_T_X_001
3.19	Summary of Grade 1 to 4 Related Adverse Events Modified Treated Subjects	Table S.6.5.1E / rt-ae-relateds1.lst / GS_AE_T_X_001

CONFIDENTIAL

AI468038/205891

Number	Title	BMS Table number/File Name/BMS Template
3.20	Summary of Grade 2 to 4 Related Adverse Events Modified Treated Subjects	Table S.6.5.1F / rt-ae-relgrade2to4s1.lst / GS_AE_T_X_001
3.21	Summary of Grade 3 to 4 Related Adverse Events Modified Treated Subjects	Table S.6.5.1G / rt-ae-relgrade3to4s1.lst / GS_AE_T_X_001
3.22	Summary of CDC Class C AIDS Events Modified Treated Subjects	Table S.6.4.1A / rt-ae-cdcaes1.lst / GS_AE_T_X_001
3.23	Listing of Adverse Event CDC Class C AIDS Events Modified Treated Subjects	Table S.6.4.1B / rl-ae-cdcaes1.lst / GS_AE_L_X_001
3.24	Summary of Gastrointestinal Events of Special Interest Modified Treated Subjects	Table S.6.4.1C / rt-ae-giaes1.lst / GS_AE_T_X_001
3.25	Listing of Adverse Event Gastrointestinal Events of Special Interest Modified Treated Subjects	Table S.6.4.1D / rl-ae-giaes1.lst / GS_AE_L_X_001
3.26	Summary of Worst Toxicity Grade Modified Treated Subjects	Table S.7.1.1A / rt-lb-toxs1.lst / SS_LB_T_001
3.27	Summary of Grade 3-4 Toxicity Modified Treated Subjects	Table S.7.1.1B / rt-lb-g34toxs1.lst / SS_LB_T_001
3.28	Summary of Treatment-Emergent Abnormalities Modified Treated Subjects	Table S.7.1.1C / rt-lb-etoxs1.lst / SS_LB_T_001
3.29	Summary Statistics for Renal Function Values and Change from Baseline - SI Units Modified Treated Subjects	Table S.7.2.1A / rt-lb-renals1.lst / SS_VL_T_006

CONFIDENTIAL

AI468038/205891

Number	Title	BMS Table number/File Name/BMS Template
3.30	Summary Statistics for Renal Function Values and Change from Baseline - US Units Modified Treated Subjects	Table S.7.2.1B / rt-zl-renals1.lst / SS_VL_T_006
3.31	Summary Statistics for Fasting Lipid Values and Change from Baseline - SI Units Modified Treated Subjects	Table S.7.2.1C / rt-lb-lipidss1.lst / SS_VL_T_006
3.32	Summary Statistics for Fasting Lipid Values and Change from Baseline - US Units Modified Treated Subjects	Table S.7.2.1D / rt-zl-lipidss1.lst / SS_VL_T_006
3.33	Summary Statistics for Fasting Lipid Values and Percent Change from Baseline - SI Units Modified Treated Subjects	Table S.7.2.1E / rt-lb-pchglipidss1.lst / SS_VL_T_006

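### The 30-day post-dose allowance for safety data lets off-drug laboratory, lipid, ECG and vital-sign values enter the by-visit means as on-treatment values

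*SAP*

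**What the plan says.** Section 8.1.2 sets the on-treatment limits: "On-treatment parameters are derived from measurements after the start of study therapy through the last dose of study therapy plus 4 days for efficacy". The same limit applies to biomarkers and to the outcomes scales. The longer limits follow: "plus 10 days for resistance parameters and plus 30 days for safety". Within a visit window the choice rests on distance alone: "if a subject has more than one measurement included within a window, the assessment closest to the target day will be used".

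The by-visit safety summaries draw on these rules. Section 7.6.13.2 states "All summaries of laboratory data over time will use observed values" and "Observed values and changes from baseline in creatinine and creatinine clearance will be summarized at each scheduled visit by treatment arm". It treats fasting lipids the same way, and the only values it removes are lipid values after lipid-reducing agents start. Sections 7.6.14 (ECG) and 7.6.15 (vital signs) also summarize observed values over time. The laboratory and vital-sign sections point to the Section 8 windows. Section 7.6 applies no cut at an analysis week: "All safety data available in the database at the time of the lock will be included".

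The November 2017 final-analysis appendix keeps these outputs: renal function and lipids (Tables 3.29-3.34), ECG over time (3.43) and vital signs (3.46). Table 3.29, for example, is titled "Summary Statistics for Renal Function Values and Change from Baseline - SI Units Modified Treated Subjects". The appendix gives no new on-treatment definition.

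**The concern.** A by-visit mean change is read as the effect of treatment at that visit. If some values behind it were taken up to 30 days after the drug was stopped, the mean mixes on-drug and off-drug states. Any effect that reverses on stopping then looks smaller than it is. A subject can also be counted at a visit that he or she never reached on drug.

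The SAP's own choices point the other way in two places. Section 6.1 defines the on-treatment period as one that "begins on the first day of open-label therapy and ends after 96 weeks of dosing or early termination, whichever comes first", with no 30-day extension. Section 8.1.2 gives renal and bone biomarkers 4 days, and Section 7.7 summarizes those by visit as well. Fractional excretion of phosphorus is computed partly from serum creatinine. A sample taken 14 days after the last dose is therefore off-treatment for that biomarker and on-treatment for creatinine.

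**Working it through.** The plan states no figure on this point, so there is none to reproduce. The check applies the stated rules.

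**Inputs from the SAP.** Table 8.1.2-1, column for other parameters: Week 24 is Days 142-197 (target 169), Week 32 is Days 198-253 (target 225), Week 48 is Days 310-379 (target 337). The limit is last dose + 30 days for safety and + 4 days for biomarkers. Selection is by the smallest absolute distance to the target day.

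**Example 1: the only value in a window.**
- Last dose on Day 169, follow-up sample on Day 199.
- 169 + 30 = 199, so the sample is on-treatment.
- Day 199 lies in the Week 32 window and is the only value there. It becomes the Week 32 value of a subject who stopped at Week 24.
- With + 4 days the limit is 169 + 4 = Day 173, so the subject has no Week 32 value.

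**Example 2: displacement.**
- Last dose and a sample on Day 205, second sample on Day 235 (205 + 30 = 235, so it is on-treatment).
- Distances to target 225: |205 - 225| = 20 and |235 - 225| = 10. The off-drug value is selected.
- With + 4 days the limit is Day 209, so the Day 205 value is used.

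Neither example needs an assumption about how fast an effect reverses.

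**Effect on a mean.** Let f be the share of values in a window that are off drug, and let the effect have fully reversed in them. The mean effect is then (1 - f) times the on-drug effect: 95% of it at f = 0.05, 90% at f = 0.10. With partial reversal the loss is smaller.

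**Size of f.** The SAP does not give it. The assumptions used here are not in the documents:
- last-dose days spread evenly over Days 57-505;
- scheduled visits on their target days;
- one off-drug sample 14 or 28 days after the last dose, with or without a sample on the last-dose day;
- a varying share of subjects who give the off-drug sample.

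| Subjects with an off-drug sample | Off-drug share, Week 24 | Off-drug share, Week 48 |
|---|---|---|
| 0% | 0% | 0% |
| 10% | about 1-2% | about 2-3% |
| 100% | about 9-14% | about 16-25% |

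At 50% the shares are roughly half those in the last row. With a + 4-day limit, samples taken 5 to 30 days after the last dose contribute 0% at every level.

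**The case against.** The strongest objection is that the necessary condition is not in the document. Section 6.1 lists only a screening and a treatment period. Section 2.1 lists no visit after Week 96, and Table 8.1.2-1 has no follow-up row. If no post-treatment samples were taken, nothing happens. The protocol may schedule such a visit, but it is not at hand. This stands, and it makes the point conditional.

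The 30-day tail is also deliberate: it matches the adverse-event rule in Section 7.6.1. The study is one of estimation and the affected tables are descriptive. The by-subject listings remain, so late values can be identified. This lowers the severity, but it does not justify labelling off-drug values as on-treatment in a mean.

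A hard + 4-day cut would remove discontinuation assessments from the by-visit tables, including those of subjects whose toxicity persists. That is fair, and the fix allows for it. The mismatch between creatinine and the phosphorus biomarker has no shown numerical consequence, because the two appear in separate tables. It shows only that the limits are inconsistent.

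A reader might infer from the early end of the study, with site notice on 10 October 2016, that every subject was taken off drug and contributed an off-drug value. The final-analysis appendix does not say so. A reader might also infer that the distortion differs by arm, but that depends on stopping times the documents do not give.

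**Conclusion.** The rule as written allows off-drug safety values into by-visit means under an on-treatment label, and the selection rule does not keep them out. That follows from the text alone. The bias in the mean is conditional: it needs post-treatment samples and an effect that reverses after stopping, and then its direction is toward zero.

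The size cannot be fixed from the documents. Under the assumptions above it runs from nothing to about 9-14% of the effect at Week 24 and 16-25% at Week 48. The upper ends require a sample from every subject and full reversal by the time of that sample, so they are a ceiling for those assumptions.

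Worst-grade laboratory tables and the longest-interval and largest-change ECG categories cannot be lowered by extra values. Biomarkers already use + 4 days, and the primary endpoint is not touched. The severity is minor.

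**What to change.** In Section 8.1.2, split the safety limit by type of output:
- Keep last dose + 30 days for adverse events, worst-grade and treatment-emergent laboratory tables (3.26-3.28), and the longest-interval and largest-change ECG category tables.
- Use last dose + 4 days, the limit already set for biomarkers, for by-visit summaries of laboratory tests, lipids, ECG intervals and vital signs (3.29-3.34, 3.43, 3.46).
- Show values from Day 5 to Day 30 after the last dose in a separate post-treatment row of the same tables, so that discontinuation assessments are not lost.

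The cost is a short change to the text, one flag in the analysis data sets and one extra row in the table layouts. Some windows will hold slightly fewer values.
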